#### 4.3.2.6 Visit 5 (Day 29 ± 2 days)

At Visit 5, the following activities and assessments will be performed (**NOTE:** All ocular assessments must be performed in both eyes):

- Eye pain (VAS) – to be assessed prior to any physical evaluation
- Eye discomfort – to be assessed prior to any physical evaluation
- Photophobia (VAS) – to be assessed prior to any physical evaluation
- Vital signs examination (temperature, blood pressure and pulse) – to be completed 15 min before any ocular assessment

- Slit-lamp examination
  - ✓ Anterior chamber cell
  - ✓ Anterior chamber flare
  - ✓ Chemosis
  - ✓ Bulbar conjunctival injection
  - ✓ Ciliary injection
  - ✓ Corneal edema
  - ✓ Keratic precipitates
- IOP
- BCVA measured by Snellen chart
- Indirect ophthalmoscopy
- AE assessment (**NOTE:** Expected changes or the presence of inflammation or pain resulting from routine cataract surgery will not be captured as AEs)
- Concomitant medications

#### 4.3.2.7 Unscheduled Visit

If an unscheduled visit is necessary to follow an intercurrent event, any untoward findings related to that event should be captured as AEs and/or as concomitant therapies on source documents and relevant sections of the electronic case report form (eCRF). If the event meets the requirement for an SAE, please record on the SAE section of the eCRF and follow all SAE-related procedures (see Section [8.3.5](#)).

#### 4.3.2.8 Early Termination Visit

At any time, the investigator will make every attempt to ensure that an Early Termination Visit will be held in the case of a patient discontinuing the study (see Section 5.3).

At the Early Termination Visit, the following activities and assessments will be performed (**NOTE:** All ocular assessments must be performed in both eyes):

- Eye pain (VAS) – to be assessed prior to any physical evaluation
- Eye discomfort – to be assessed prior to any physical evaluation
- Photophobia (VAS) – to be assessed prior to any physical evaluation
- Vital signs examination (temperature, blood pressure and pulse) – to be completed 15 min before any ocular assessment
- Physical and eye examination
- Slit-lamp examination
  - ✓ Anterior chamber cell
  - ✓ Anterior chamber flare
  - ✓ Chemosis
  - ✓ Bulbar conjunctival injection

- ✓ Ciliary injection
- ✓ Corneal edema
- ✓ Keratic precipitates
- IOP
- BCVA measured by Snellen chart
- Indirect ophthalmoscopy
- Review and return of the patient diary
- Return of the remaining study medication
- AE assessment (**NOTE:** Expected changes or the presence of inflammation or pain resulting from routine cataract surgery will not be captured as AEs)
- Concomitant medications

#### **4.3.3 *Study Period***

The anticipated first patient in (FPI) is 1Q 2020 and the planned last patient last visit (LPLV) is 4Q 2020.

#### **4.3.4 *Study Termination***

The end of study is defined as the date of the LPLV.

---

## 5. STUDY POPULATION

### 5.1 Inclusion Criteria

Patients will be eligible for study participation if they meet all of the following criteria:

- 1) Male or female, age 18 years or older on day of consent
- 2) Patients with routine unilateral cataract surgery on the day prior to study randomization
- 3) Patients with at least 5 cells in anterior chamber on the first day after surgery (at Visit 1)
- 4) Willing and able to understand and provide written ICF (at Visit -1)
- 5) Women who satisfy one of the following:
  - a) Are of child-bearing potential who are not pregnant or lactating and who are either abstinent or sexually active on an acceptable method of birth control (methods that can achieve a failure rate of less than 1% per year when used consistently and correctly, like hormonal contraception (oral pills, implantable device, or skin patch), intrauterine device, bilateral tubal occlusion, or double barrier) for at least 4 weeks prior to Visit 1 and throughout the study (i.e., until Day 29),  
OR
  - b) Are post-menopausal (have had no menstrual cycle for at least one year prior to Visit -1) or have undergone a sterilization procedure (bilateral tubal ligation, hysterectomy, hysterectomy with unilateral or bilateral oophorectomy or bilateral oophorectomy) at least 6 months prior to Visit -1

### 5.2 Exclusion Criteria

The patients meeting any of the following criteria will not be permitted to enter the study:

- 1) Systemic administration of any corticosteroid or immunosuppressant drugs in the previous 2 weeks prior to the first instillation of the IMP
- 2) Periocular injection in the study eye of any corticosteroid solution within 4 weeks prior to the first instillation of the IMP, or of any corticosteroid depot within 2 months prior to the first instillation of the IMP (Ozurdex® [dexamethasone]: within prior 6 months; Iluvien® [fluocinolone]: within prior 36 months).
- 3) Instillation of any topical ocular corticosteroid, NSAID, mast cells stabilizers, antihistamines or decongestants within 2 weeks prior to the first instillation of the IMP, except pre-surgical and/or surgical administration of 1 drop of a topical NSAID or corticosteroid, at the investigator discretion
- 4) Prescription of any topical ocular medication, except preservative-free antibiotics for prophylactic purposes
- 5) Any history of glaucoma or ocular hypertension in the study eye
- 6) History or presence of endogenous uveitis
- 7) Any current corneal abrasion or ulceration
- 8) Any confirmed or suspected active viral, bacterial, or fungal keratoconjunctival disease
- 9) Known hypersensitivity or contraindication to the study drug or any of its components
- 10) History of steroid-related IOP increase

- 11) Previous surgery in the last 4 weeks prior to the Screening visit (Visit -1) or new surgery scheduled to be performed before the end of the study period on the contralateral eye
- 12) Presence of ocular hemorrhage which interferes with the evaluation of post-surgery inflammation
- 13) Presence of intraoperative complications during the cataract surgical procedure that may increase post-operative inflammation; this includes, in particular, patients with ocular hemorrhage, floppy iris syndrome, increased IOP ( $\geq 24$  mmHg), posterior capsule rupture and injections of gas into the vitreous body
- 14) Increased cumulative dissipated energy value during phacoemulsification (increased energy used for phacoemulsification exert additional stress on iris and other anterior chamber structures and may generate excessive inflammation)
- 15) Presence of zonular dialysis (rupture of zonular fibers that attach lens to the ciliar body which may lead to partial luxation of the lens / lens capsule and is a serious complication of cataract surgery)
- 16) Presence of Fuchs' endothelial dystrophy (loss of endothelial cells that may result in chronic corneal edema after cataract surgery especially if high energy was used during phacoemulsification)
- 17) Presence of *cornea guttata*
- 18) Pupil dilation lower than 4.5 mm
- 19) Presence of lower lacrimal duct obstruction and/or history of infectious dacryocystitis
- 20) Presence of IOP  $\geq 24$  mmHg in the study eye at Visit 1
- 21) Participation in any study of an investigational topical or systemic new drug or device within 30 days prior to the Screening visit (Visit -1), or at any time during the study
- 22) Prior participation in the study described in this protocol, unless patient was not randomized
- 23) In the opinion of the investigator or study coordinator, be unwilling or unable to comply with study protocol or unable to successfully instill eye drops
- 24) Disease, condition (including monocular patients), or disorder that in the judgement of Investigator could confound study assessments or limit compliance to study protocol

### 5.2.1 **Restrictions**

Patients will be permitted to continue all their current ocular treatments, including the use of artificial tears, eyelid massage, or warm compresses, if they commit to using the same brand/regimen throughout the study.

None of the ocular treatments, whether over the counter (OTC) or prescription or study medication, should be used within 5 minutes of another ocular treatment during the study. Study medication should not be used within 30 minutes prior to any study visit.

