## 6.7 Prior and Concomitant Medications

All medications (including OTC, vitamins, and antacids) taken 2 months prior to Screening visit (Visit -1) (36 months prior for ocular implants and/or intravitreal injections) and throughout the study duration, must be recorded on the eCRF. The generic name of the drug, dose, route of administration, duration of treatment (including start and stop dates), frequency, indication, and whether or not the medication was taken due to an AE will be recorded for each medication.

Patients will be asked to phone the study center at any time to speak to a member of the medical personnel should they require any concomitant medication.

Medication, which is considered necessary for the patient safety and well-being, may be given at the discretion of the investigator. However, concomitant medication administered during the study may lead to withdrawal of the patient from the IMP (Section [6.7.1](#)).

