### 6.7.1 Prohibited Concomitant Medications

The use of the following medications is not permitted during the study:

- Any systemic or local therapy with corticosteroids (other than the study drug) or immunosuppressant (except pre-surgical and/or surgical administration of 1 drop of a topical NSAID or corticosteroid, at the investigator discretion)
- Any topical ocular medication (except preservative-free antibiotics for prophylactic purposes and preservative-free artificial tears).
- Any systemic NSAID or opioids drugs (except occasional use of OTC formulations titrated no more than one single dose per week)

The aforementioned medications will be considered as rescue medications when administered in patients not responding to the IMP (Section [6.7.2](#)).

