### 10.4 Protocol Deviations

The classification of protocol deviations in major or minor deviations will be mutually agreed between the Sponsor and [REDACTED] at the start of the study.

A major protocol deviation occurs when the patient, investigator, or Sponsor fails to adhere to significant protocol requirements affecting selection criteria, administration of study treatment and administration of prohibited medication.

Failure to comply with GCP guidelines will also result in a major protocol deviation. The Sponsor will determine if a major protocol deviation will result in withdrawal of a patient.

Deviations to the study protocol will be documented in a Protocol Deviation Log.

The Sponsor or delegate is responsible for immediately reporting major deviations according to applicable regulations, as well as deviations from the study protocol that substantially affect the integrity or the safety of the patients or the scientific validity of the study, to the CA.

Protocol deviations will be reviewed during a meeting before database lock in order to allocate the patients into the different analysis sets.

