Rescue medication shall be as reported as such in the eCRD. The following ATC3 codes of concomitant medication will be considered as prohibited medication if they are not classified as rescue medication (all medications will be reviewed and it will be considered whether any medication should be included or excluded in the prohibited classification):

- D07A - Corticosteroids, plain
- D07B - Corticosteroids, combinations with antiseptics
- D07C - Corticosteroids, combinations with antibiotics
- D07X - Corticosteroids, other combinations
- G01B - Combinations of corticosteroids and antiinfectives for gynaecological use
- A01AC - Corticosteroids for local oral treatment
- D01A - Corticosteroids in combination with antifungals
- D10AA - Corticosteroids, combinations for treatment of acne
- C05AA - Antihemorrhoidals with corticosteroids
- S01B – Antiinflammatory agents
- S02B - Corticosteroids
- S02C - Corticosteroids and antiinfectives in combination
- S03B - Corticosteroids
- S03C - Corticosteroids and antiinfectives in combination.
- H02 - Corticosteroids for systemic use.
- L04A - Immunosuppressants
- M01A - Antiinflammatory and antirheumatic product, non-steroids
- N02BE - NSAIDs in combination with paracetamol.
- M01B - Salicylates in combination with corticosteroids.
- M01B - Combinations of antiinflammatory/antirheumatic agents
- N02A - Opioids
- Any ATC3 with ocular route except for S01A, S03A (Antiinfectives) preservative-free for prophylactic purposes and S01X (Other ophthalmologicals) preservative-free.

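### Protocol 5.2.1 lets patients continue any artificial tears, but 6.7.1 and SAP 6.3.9 prohibit preserved ones; unless a review excuses the product, a compliant patient can lose Day 8

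*Protocol*

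**What the plan says.** - **Permission.** Protocol 5.2.1: "Patients will be permitted to continue all their current ocular treatments, including the use of artificial tears, eyelid massage, or warm compresses". The condition is an unchanged brand and regimen for the whole study. The section sets no preservative-free limit and does not refer to 6.7.1.
- **Prohibition.** Protocol 6.7.1 bars "Any topical ocular medication (except preservative-free antibiotics for prophylactic purposes and preservative-free artificial tears"). SAP 6.3.9 turns this into a coding rule; its prohibited list ends with "Any ATC3 with ocular route except for S01A, S03A (Antiinfectives) preservative-free for prophylactic purposes and S01X (Other ophthalmologicals) preservative-free".
- **Recording.** Protocol 6.7 requires on the eCRF "All medications (including OTC, vitamins, and antacids) taken 2 months prior to Screening visit" and those taken during the study, so self-bought tears are captured.
- **Eligibility.** Exclusion 3 covers "Instillation of any topical ocular corticosteroid, NSAID, mast cells stabilizers, antihistamines or decongestants within 2 weeks prior to the first instillation of the IMP". Exclusion 4 covers "Prescription of any topical ocular medication, except preservative-free antibiotics for prophylactic purposes".
- **Consequence.** SAP section 5 limits the FAS efficacy analyses to visits on study product and free of prohibited or rescue medication. It also bars such use up to Visit 3 in the Visit 3 PP set. Protocol 10.4 calls it a major deviation when someone "fails to adhere to significant protocol requirements affecting selection criteria, administration of study treatment and administration of prohibited medication".
- **Safeguard.** SAP 6.3.9 adds that all medications will be reviewed and "it will be considered whether any medication should be included or excluded in the prohibited classification". SAP 6.2 plans a blind review of major and critical deviations before unblinding.

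**The concern.** Two rules in force give opposite instructions for the same bottle. The same-brand condition in 5.2.1 holds a user of preserved tears to that product, and 6.7.1 forbids it. A site that follows 5.2.1 then creates the deviation that 10.4 treats as major.

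What is at stake is the patient's Day 8 visit, which carries both the primary and the key secondary endpoint, and the patient's place in the Visit 3 PP set. The SAP also points two ways on the FAS. Section 5 removes visits with prohibited medication from the efficacy analyses, while the primary test in 6.3.5 conditions only on rescue. Under 6.7.1 a prohibited product becomes rescue when it is given for non-response, so tears carried over from before randomization are not rescue. Losing the FAS visit therefore rests on the section 5 sentence alone.

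**Working it through.** **Step 1: who is caught.** Eyelid massage and warm compresses are not medication. Preservative-free tears are exempt in 6.7.1 and in SAP 6.3.9. Exclusion 3 removes recent users of steroid, NSAID, mast cell stabilizer, antihistamine and decongestant drops but does not name tears. Exclusion 4 is worded for prescribed products. What remains is mainly over-the-counter preserved tears. Their user passes exclusions 3 and 4, obeys 5.2.1, is recorded under 6.7, and meets the prohibited definition in SAP 6.3.9.

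**Step 2: the plan's own figure.** Inputs from protocol 9.1.1: 0.22 against 0.07, two-sided 0.05, 80% power, 2:1, 202 evaluable, 4% loss, 210 randomized. For the uncorrected chi-square test, power = Φ[(Δ − 1.96·SE₀)/SE₁]. At 135/67:
- pooled proportion = (135 × 0.22 + 67 × 0.07)/202 = 0.170
- SE₀ = √[0.170 × 0.830 × (1/135 + 1/67)] = 0.0562
- SE₁ = √[0.22 × 0.78/135 + 0.07 × 0.93/67] = 0.0474
- power = Φ[(0.15 − 0.1101)/0.0474] = Φ(0.84) = 80.0%

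The odds ratio is (0.22/0.78)/(0.07/0.93) = 3.747, as stated. 202/0.96 = 210.4, against the stated 210. The plan's figures are reproduced.

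**Step 3: loss of Day 8 visits.** The share affected is assumed: 1% of 202 is about 2 patients, 5% about 10. Two treatments of a dropped visit are possible, because the documents disagree. SAP 6.6 foresees no imputation, so the visit is left out. The protocol synopsis assigns failure to patients with missing primary data, so each response rate is multiplied by (1 − f), where f is the share affected. Normal approximation at exact 2:1:

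| Share affected | Power, left out | Power, counted as failure | Expected difference, left out | Expected difference, failure |
|---|---|---|---|---|
| 0% | 80.2% | 80.2% | 15.0 | 15.0 |
| 1% | 79.7% | 79.6% | 15.0 | 15.0 × 0.99 = 14.85 |
| 2% | 79.3% | 79.1% | 15.0 | 15.0 × 0.98 = 14.70 |
| 5% | 77.9% | 77.4% | 15.0 | 15.0 × 0.95 = 14.25 |

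The left-out columns assume that tear users respond like other patients.

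**Step 4: exact check.** Full enumeration of the two binomials at 135/67 gives 82.0% with nobody affected. With failures it gives 81.5% at 1% and 79.4% at 5%. With ten visits left out (128/64) it gives 80.4%, and the 95% interval half-width for the difference goes from 9.28 to 9.52 points.

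Exact power moves unevenly because the test is discrete. Eight visits lost gives 80.44% as 129/65 but 79.63% as 130/64. No particular patient count can therefore be named as the point where 80% is lost.

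Across methods, the cost is roughly 0.5 points at 1% and 2.5 points at 5%. The largest value is 80.2 − 77.4 = 2.8, from the approximation with failures at 5%.

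**The case against.** The strongest reply is that the plan already has the machinery to deal with this. SAP 6.3.9 has every medication reviewed for the prohibited class, and that step comes before section 5 applies. Protocol 10.4 has the major or minor grading agreed at study start, and deviations are reviewed before database lock. The study product itself contains benzalkonium chloride in both arms (protocol 6.1), so a reviewer would have good reason to excuse a patient who followed 5.2.1. The primary test mentions only rescue.

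Most of this stands, and it is why the point is minor: a FAS visit is lost only if the review does not excuse the product. It does not remove the conflict. Neither review refers to the 5.2.1 permission or gives a criterion for this case, and no rule says that 6.7.1 overrides 5.2.1, which names artificial tears expressly.

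A reader might go further and infer any of the following. The documents support none of them.
- *Everything permitted in 5.2.1 is later prohibited.* Step 1 shows that only a narrow group is caught.
- *The loss biases the comparison.* The use predates randomization, and the same rule applies to both arms under masking. Counting failures would shrink the difference slightly but would not favour an arm.
- *Power falls below 80% at a definite number of users.* That depends on how the losses split between the arms.

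**Conclusion.** The inconsistency is real and minor. A patient on over-the-counter preserved tears who does what 5.2.1 allows breaches 6.7.1. Unless excused on review, that patient loses Day 8 in the FAS under SAP section 5 and a place in the Visit 3 PP set.

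The number of such patients is unknown and probably small. On the assumed 1% to 5%, the cost is about half a point to two and a half points of power, with at most 0.75 points (15.0 − 14.25) off the expected difference, and then only under the synopsis failure rule. The primary conclusion is not threatened. The avoidable harm is deviations charged to compliant patients and a Day 8 rule left to case-by-case judgement.

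**What to change.** 1. **Protocol 5.2.1.** Limit continued ocular treatments to non-drug measures (eyelid massage, warm compresses) and the products that 6.7.1 exempts, with a cross-reference to 6.7.1.
2. **SAP 6.3.9.** State that preserved artificial tears continued unchanged from before randomization, under 5.2.1 as it now reads, are not classed as prohibited medication for the section 5 FAS visit rule. Alternatively, write that exception into the section 5 sentence itself. A sentence in 6.3.9 that only says the visits are kept, without declassifying the product, would contradict section 5.
3. **PP set.** Leave assignment to the masked review.

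The cost is one sentence in each document, settled before unmasking. Exclusion 4, the visit schedule and the sample size do not change.

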### 5.3 **Withdrawal, Premature Discontinuation of Study Medication, and Replacement of Patients**

Patients are free to discontinue their participation in the study at any time. Additionally, patients may be withdrawn from study at any time, if deemed necessary by the investigator

(after discussion with the Medical Monitor). Withdrawal from the study will not affect or prejudice the patients' further care or treatment.

Potential reasons for withdrawal of patients from this study are:

- The decision of a patient to withdraw informed consent
- Patient is lost to follow-up (Section [5.3.1](#))
- Potential reasons for premature discontinuation of study medication include, but are not limited to: Occurrence of a treatment-emergent AE (TEAE) or considerable worsening of an AE that, in the opinion of the investigator in consultation with the Medical Monitor and Sponsor, represents an unacceptable risk to the patient if he/she continues to receive study medication. The investigator must follow the patient until the AE resolves or satisfactorily stabilizes
- Administration of a rescue medication. Any patient placed on rescue therapy will discontinue the use of the IMP (see Sections [6.7.1](#) and [6.7.2](#))
- Patient's failure to comply with protocol requirements or study related procedures
- In case of pregnancy. The investigator will continue the follow-up of the patient until the end of the pregnancy
- Any surgery (different from the actual routine cataract surgery on the study eye) in the study or contralateral eye

In any case of premature discontinuation of study medication, the investigator must make extensive efforts to ensure that the patient will attend all his/her remaining study visits until study completion (at Visit 5), aiming to collect the most complete efficacy and safety data.

The reason and date the patient is withdrawn from the study will be documented in the eCRF (e.g. lost to follow-up, consent withdrawn, AEs, etc.).

If a patient is withdrawn from the study, the investigator should attempt to complete all discharge procedures (including the Early Termination Visit; Section [4.3.2.8](#)). All AEs should be followed up according to Section [8.3.6](#).

If a patient is withdrawn from the study, or withdraw his/her consent, all data collected until the time of withdrawal will be used in the analyses, unless this is prohibited by local regulations.

Patients who drop out from the study will not be replaced.

### **5.3.1 Lost to Follow-up**

A patient will be considered lost to follow-up if he/she fails to return for 2 consecutive scheduled visits and is unable to be contacted by the study center.

The following actions must be taken if a patient fails to return to the center for a required study visit:

- The center must attempt to contact the patient and reschedule the missed visit as soon as possible and counsel the patient on the importance of maintaining the assigned visit schedule and ascertain whether or not the participant wishes to and/or should continue in the study.

- Before a patient is deemed lost to follow up, the investigator or designee must make every effort to regain contact with the patient (where possible, 3 telephone calls and, if necessary, a certified letter to the patient's last known mailing address or local equivalent methods). These contact attempts should be documented in the patient's medical record.
- Should the patient continue to be unreachable, he/she will be considered to have withdrawn from the study with a primary reason of lost to follow-up.

